4.8.1.1 Analysis Populations

Intent-to-Treat (ITT) Population: all subjects that are randomized, analyzed according to randomized treatment assignment.

As-treated Population: all randomized subjects who receive any investigational product.

Subjects who receive any dose of MEDI6012 will be assigned to MEDI6012 group. Subjects who receive only placebo doses will be analyzed with the placebo group; conversely, subjects who receive any dose of MEDI6012 will be analyzed with the MEDI6012 group. Safety analyses will be performed on the As-treated Population.

Primary Efficacy Analysis Population: all randomized subjects who receive at [REDACTED] doses of investigational product with [REDACTED]. Subjects who receive only placebo doses will be analyzed with the placebo group; conversely, subjects who receive 2 or more doses of MEDI6012 will be analyzed with the MEDI6012 group.

Efficacy Analysis Population [REDACTED]: all randomized subjects who receive at least two doses of investigational product with [REDACTED]. Subjects who receive only placebo doses will be analyzed with the placebo group; conversely, subjects who receive 2 or more doses of MEDI6012 will be analyzed with the MEDI6012 group.

Efficacy Analysis Population [REDACTED]: all randomized subjects who receive at least two doses of investigational product with [REDACTED]. Subjects who receive only placebo doses will be analyzed with the placebo group; conversely, subjects who receive 2 or more doses of MEDI6012 will be analyzed with the MEDI6012 group.

CTA Analysis Population: randomized subjects in [REDACTED] who receive a full treatment course of investigational product and are eligible for coronary CTA and have 1 or more CTA performed. The subjects who receive [REDACTED] placebo doses will be analyzed with the placebo group; conversely, subjects who receive [REDACTED] doses of MEDI6012 will be analyzed with the MEDI6012 group.

Immunogenicity Population: all subjects in the As-treated Population who have at least one serum sample for immunogenicity testing.

PK Population: all subjects in the As-treated Population who have at least one detectable serum concentration measurement for LCAT mass or activity.

4.8.2 Sample Size

A total of 90 subjects per arm will provide 80% power to detect a [REDACTED] reduction in infarct size between MEDI6012 [REDACTED] group and combined placebo group ([REDACTED] placebo groups), and between MEDI6012 [REDACTED] group and combined placebo group with one-sided alpha 0.05 assuming a coefficient of variation of [REDACTED]. A total of 180 subjects per arm is

required as a █% rate of exclusion from the primary efficacy analysis population is expected due to █ in the infarct-related artery on initial angiography and other reasons for subsequent exclusion or drop-out (Botker et al, 2010; Hausenloy et al, 2013). A █ reduction in infarct size is thought to be clinically significant, assuming it would equate to an approximate █% absolute reduction in infarct size in a future trial that enrolls subjects with large infarcts. A █% absolute reduction in infarct size is associated with a █% relative risk reduction in heart failure and mortality. With this same sample size, the power to detect a █% absolute difference in EF between each MEDI6012 group and combined placebo group with █ alpha █ is > █% assuming standard deviation █%. For the secondary endpoint of non-calcified coronary plaque regression/progression, there will be > █% power to detect a █ mm³ change in NCPV from index CTA to the 10-12 week CTA between MEDI6012 group and placebo group with █ assuming a common standard deviation of █ mm³ and █% drop-out. It is estimated that the study will involve approximately 43 sites in approximately 10 countries.

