500	[REDACTED]
501	[REDACTED]
502	[REDACTED]
503	[REDACTED]
504	[REDACTED]
505	[REDACTED]
506	[REDACTED]
507	[REDACTED]
508	[REDACTED]
509	[REDACTED]
510	[REDACTED]
511	[REDACTED]
512	[REDACTED]
513	[REDACTED]
514	[REDACTED]
515	[REDACTED]
516	[REDACTED]
517	[REDACTED]
518	[REDACTED]
519	[REDACTED]
520	[REDACTED]
521	[REDACTED]
522	[REDACTED]
523	[REDACTED]
524	[REDACTED]
525	[REDACTED]
526	[REDACTED]
527	[REDACTED]
528	[REDACTED]
529	[REDACTED]
530	[REDACTED]
531	[REDACTED]
532	[REDACTED]
533	[REDACTED]
534	[REDACTED]
535	[REDACTED]
536	[REDACTED]
537	[REDACTED]
538	[REDACTED]
539	[REDACTED]
540	[REDACTED] 30% decrease from baseline in HDL-C or a neutralizing antibody (nAb) is present, the subject will return for additional assessments. Safety data for subjects ongoing in Extended Follow-up at database lock will be reported in a clinical study report (CSR) addendum.

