3.1.1 Overview

This is a Phase 2b, randomized, placebo-controlled study to evaluate the efficacy, safety, PK/PD, and immunogenicity of repeat doses of MEDI6012 in adult subjects presenting with acute STEMI. In this study, the subject and MedImmune staff will be blinded. Sites will be trained to keep the investigator blinded. However, due to the acute nature of the study, members of the research team and, possibly, the investigator may be unblinded.

Approximately 540 subjects are planned to be randomized across approximately 43 study sites in around 10 countries to evaluate a [REDACTED] regimen and a [REDACTED] regimen of MEDI6012.

Due to the acute nature of this study, there will be a very short screening period. The study will enroll subjects presenting with acute STEMI within 6 hours of symptom onset who are planned for emergent pPCI. After obtaining verbal or written informed consent (as per local regulations), subjects will be assessed for eligibility and, if considered eligible, will be randomized in a 1:1 ratio into either Cohort A ([REDACTED]) or Cohort B ([REDACTED]) (Figure 3). Within each cohort/dose regimen, subjects will be randomized in a 2:1 ratio to receive MEDI6012 or placebo prior to pPCI. In the event a dose regimen (Cohort A or Cohort B) is dropped at the interim analysis, subjects will be randomized in a 1:1 ratio to receive MEDI6012 or placebo for the remaining dose regimen.

Figure 3 Overall Study Schema

CMR = cardiovascular magnetic resonance (imaging); CTA = computed tomography angiography; D = study day; N = number of subjects; pPCI = primary percutaneous coronary intervention; STEMI = ST elevation myocardial infarction.

Inpatient Phase – Cohorts A and B

Both Cohorts A and B will receive their [REDACTED] doses in the inpatient setting.

[figure not shown]

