3.1.2 Treatment Regimen

Enrolment of approximately 540 subjects is planned to evaluate the █ dosing regimens (Cohort A: █ regimen and Cohort B: █ regimen) as follows:

Cohort A

- MEDI6012, █ (n ~ 180)
- Placebo, █ (n ~ 90)

Cohort B

- MEDI6012, █ (n ~ 180)
- Placebo, █ (n ~ 90)

Inpatient Phase Dosing

Both Cohort A and Cohort B inpatient dosing will consist of a [REDACTED] loading dose of Investigational Product administered on Day 1, followed on Day 3 by a [REDACTED] second dose, both administered in the inpatient setting ([Table 6](#) and [Table 7](#)). Dosing for Cohort A will be completed at this point.

Table 6 Dosing for Cohort A: [REDACTED] Regimen

Day	Dose	Route	Time
1	[REDACTED]	[REDACTED]	[REDACTED]
3	[REDACTED]	[REDACTED]	[REDACTED]
10, 17, 24, 31	[REDACTED]	[REDACTED]	[REDACTED]
10, 17, 24, 31	[REDACTED]	[REDACTED]	[REDACTED]

For Cohort B, additional maintenance doses of [REDACTED] mg will be administered at weekly intervals on Days 10, 17, 24, and 31 ([Table 7](#)). These doses will be administered in the outpatient setting.

Table 7 Dosing for Cohort B: [REDACTED] Regimen

Day	Dose	Route	Time
1	[REDACTED]	[REDACTED]	[REDACTED]
3	[REDACTED]	[REDACTED]	[REDACTED]
10, 17, 24, 31	[REDACTED]	[REDACTED]	[REDACTED]
10, 17, 24, 31	[REDACTED]	[REDACTED]	[REDACTED]

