4.2.1.1 Study Procedure Modifications in Response to the COVID-19 Pandemic

The modifications listed below are designed to enable safety monitoring of subjects enrolled in the trial through an extended blood sampling window as well as to maintain trial integrity for the primary and secondary endpoints by enrolling all remaining patients in Cohort B (to obtain both the CMR and CTA as well as extended dosing data), which has had a greater dropout rate further impacted by COVID-19.

- 1 If the Visit 6 (Day 70-84) follow-up visit cannot be conducted in person due to the coronavirus disease (COVID-19) pandemic, the following study procedure modifications are permissible:
 - (a) Where possible, a subject should return to the clinic as soon as possible after the planned Visit 6 (Day 70-84) visit but no more than 150 days post dose 1 for blood sample collection (except for future use samples), including immunogenicity, PK, and PD, as listed in the Schedule of Study Procedures ([Table 8](#) and [Table 9](#)) for Day 70-84.
 - (b) However, assessment of AEs/SAEs and concomitant medications should be done via telephone contact within the originally specified window for Visit 6 (ie, Day 70-84).
 - (c) If a subject returns to the clinic for blood sample collection within the extended window, any AEs/SAEs that occur between the telephone contact and the date of this visit should also be recorded.

The modifications in study procedures listed above (1a-c) are only permitted due to COVID-19-related constraints impacting the subject, site, or health system; otherwise, the study procedures should be conducted within the timeframes originally specified in the Schedule of Study Procedures ([Table 8](#) and [Table 9](#)).

- 2 All subjects will be randomized into Cohort B [REDACTED] Regimen). Subjects will be randomized in a 1:1 ratio to receive MEDI6012 or placebo. This modification will remain in place until the end of the study.

Table 8 Treatment Period and Follow-up Procedures: Cohort A (Red Regimen)

Study Period	Treatment Period										Follow-up	
Visit Number	V1 (Inpatient)							V2	V3	V4	V5	V6
Procedure / Study Day	Day 1					Anytime between Days 1-3	Day 3 (48 ± 8 hours)	Day 10 (±1 day) Phone	Day 17 (± 1 day)	Day 24 (± 1 day) Phone	Day 31 (± 1 day)	Days 70-84 ^a
	Screening	Pre-PCI										
Written or verbal informed consent	X											
Verify eligibility criteria	X											
Screening ECG (clinical) ^b	X											
Abbreviated medical history review	X											

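### The switch of all remaining subjects to Cohort B at 1:1 was not carried into the stated arm sizes or the single 80% power for both regimens

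*Protocol*

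**What the plan says.** **Sample size.** Protocol 4.8.2 states "A total of 90 subjects per arm will provide 80% power to detect a" given reduction in infarct size (the value is redacted), one-sided alpha 0.05. It applies this to each regimen against placebo combined over cohorts. It then says "A total of 180 subjects per arm is" required, to allow for exclusions. SAP section 4 gives the assumed exclusion rate behind the revised sample size as 50%.

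**Arm sizes.** Protocol 3.1.2 opens with "Enrolment of approximately 540 subjects is planned to evaluate the" two regimens, and lists about 180 MEDI6012 and 90 placebo in each cohort. Protocol 4.6.1 repeats these numbers.

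**Allocation in the general text.** The synopsis describes 1:1 randomisation to a regimen, with subjects then "randomized within that dose regimen to a 2:1 ratio to receive MEDI6012 or placebo". Protocol 3.1.1, Protocol 4.6.1 and SAP 2.2 and 2.3 say the same. Apart from 4.2.1.1, the only 1:1 treatment allocation is conditional: it applies if a regimen "is dropped at the interim analysis, subjects will be randomized in a 1:1 ratio to receive MEDI6012 or placebo for the remaining dose regimen" (Protocol 3.1.1, with equivalent text in 4.6.1 and SAP 2.2 and 2.3).

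**Allocation in the COVID-19 section.** Protocol 4.2.1.1 says "All subjects will be randomized into Cohort B", 1:1 MEDI6012 to placebo, and "This modification will remain in place until the end of the study". One reason given is the state of Cohort B, "which has had a greater dropout rate further impacted by COVID-19".

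**The concern.** Section 4.2.1.1 is operative text in the same protocol version as 3.1.2, 4.6.1 and 4.8.2. Its switch is not the conditional one described elsewhere, because it does not depend on a regimen being dropped at an interim analysis. Once anyone is randomised under it, Cohort A stops growing, while Cohort B and the pooled placebo group take all further subjects. The readable text does not restate arm sizes or power to match. SAP version 3.0, dated 03Dec2020, came after Amendment 6 (04May2020), yet it still describes the 1:1 and 2:1 scheme, and its COVID-19 section (3.9) does not mention the allocation change.

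What is at stake is interpretation. Section 4.8.2 presents two equally sized, equally powered comparisons. A non-significant Cohort A result could be read against an 80% figure that may not apply to that comparison. Point estimates and confidence intervals are not affected.

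**Working it through.** **Step 1. Reproduce the plan's figures.**
- Randomised per arm: 90 / (1 − 0.50) = 180.
- Comparison arms: Cohort A active, Cohort B active and combined placebo, so 3 × 180 = 540.
- Second interim: 60% of 3 × 90 = 270 is 162, as in Protocol 4.8.8 and SAP section 4.

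The design before the switch is internally consistent.

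**Step 2. Recover the implied effect.** The effect and the coefficient of variation are redacted in 4.8.2, so the 80% cannot be recomputed from them. It can be inverted. At 90 against 90, one-sided alpha 0.05 and 80% power, the noncentrality is 1.6449 + 0.8416 = 2.4865. That is a standardised difference of 2.4865 × √(2/90) = 0.371 on the log scale.

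**Step 3. Arm sizes under 4.2.1.1.** Let N1 be the number randomised at the switch (not given) and T the final total. The expected numbers randomised are:
- Cohort A active: N1/3; Cohort A placebo: N1/6
- Cohort B active: N1/3 + (T − N1)/2; Cohort B placebo: N1/6 + (T − N1)/2
- Combined placebo: N1/3 + (T − N1)/2

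At T = 540, Cohort A active equals 180 only if N1 = 540, that is, if nobody is randomised under 4.2.1.1.

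**Step 4. Power.** With evaluable numbers nActive and nPlacebo (pooled over cohorts):

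Power = Φ(2.4865 × √[(2/90) / (1/nActive + 1/nPlacebo)] − 1.6449)

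Worked case: N1 = 400, T = 540, 50% evaluable. Cohort A active is 133.3 randomised and 66.7 evaluable. Combined placebo is 133.3 + 70 = 203.3 randomised and 101.7 evaluable. The root is 0.946, so power = Φ(2.4865 × 0.946 − 1.6449) = 76.0%.

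| N1 (assumed) | A active | B active | Combined placebo | Power A | Power B |
|---|---|---|---|---|---|
| 300 | 100 | 220 | 220 | 70.1% | 86.5% |
| 400 | 133 | 203 | 203 | 76.0% | 84.1% |
| 450 | 150 | 195 | 195 | 77.9% | 82.7% |
| 500 | 167 | 187 | 187 | 79.2% | 81.3% |

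Cohort A reaches 78.0% at N1 of about 453. A noncentral-t calculation agrees within 0.1 point.

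**Step 5. Conditions that would remove the shortfall.**

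| N1 | Power A if 60% of Cohort A (active and placebo) and 50% of Cohort B are evaluable, T = 540 | Cohort A evaluable share giving 80%, T = 540 | Total giving Cohort A 80% at 50% evaluable |
|---|---|---|---|
| 300 | 75.3% | 72% | about 1900 |
| 400 | 80.8% | 58% | about 687 |
| 450 | 82.5% | 54% | about 600 |
| 500 | 83.8% | 52% | about 558 |

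**Step 6. Sensitivity to the placebo comparator.** Steps 4 and 5 count every placebo subject towards the Cohort A comparison, as the plan's combined placebo group implies, including those randomised after Cohort A closed. With only placebo subjects randomised before the switch, and 50% evaluable, Cohort A power would be 69.0% at N1 = 400 and 77.3% at N1 = 500. The plan does not call for this comparison, so it is shown for context only.

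**The case against.** The strongest reply is that nothing in 4.8.2 is miscalculated. It is a conditional design requirement: 90 evaluable per arm give 80% power, and 180 randomised supply them. Section 4.2.1.1 then states the change plainly in the protocol body, so there is little doubt how to randomise, and the cohort sizes are marked approximate. That stands for the per-arm calculation, which reproduces. It does not cover applying one figure to both regimens after an allocation change that cannot be expected to give both the same number of subjects.

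The second reply concerns size. N1 is unknown, and nothing in the documents makes 300 more likely than 500. Equal 50% exclusion also sits awkwardly with 4.2.1.1 itself, which reports greater dropout in Cohort B. If, for illustration, 55% of Cohort A and 45% of Cohort B were evaluable at a total of 540, power for A and B would be 77.5% and 81.8% at N1 = 400, 79.4% and 80.5% at 450, and 80.8% and 79.2% at 500. From about 450 the switch would then roughly equalise power. SAP 2.2 says at least 540, and Protocol 4.1.9 allows replacement, so the total may be larger. All of this stands, and the Cohort A shortfall may be small or absent. It does not reconcile the text, because the equal arm sizes in 3.1.2 and 4.6.1 would still be out of line with 4.2.1.1.

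Third, SAP 2.4 has no readable text and the study schema figures are not shown, so a restatement there cannot be ruled out. The readable sections still need to agree with 4.2.1.1.

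Last, a null result should be judged on its observed precision more than on planned power. That is fair and limits the harm, but it is no reason to leave a planning figure standing that may not apply.

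**Conclusion.** The point holds. At a total of about 540, the cohort sizes in Protocol 3.1.2 and 4.6.1, and the single 80% power for both regimens in 4.8.2, do not follow from the allocation in 4.2.1.1. Cohort A MEDI6012 is expected to end below 180, and Cohort B MEDI6012 and combined placebo above it.

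For N1 between 300 and 500 (an assumed range), with 50% exclusion in every arm, Cohort A power runs from about 70% to 79% and Cohort B from about 87% to 81%. The inconsistency in the text does not depend on where in that range N1 fell. The power consequence does, and it also depends on the final total and on cohort-specific exclusion. The 180-per-arm figure was sound for the design before the switch. No error is claimed in the power statements for ejection fraction or plaque volume. The correction should be made.

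**What to change.** - **Protocol 3.1.2 and 4.6.1:** restate the expected arm sizes from the actual number randomised at the switch, and cross-refer to 4.2.1.1.
- **Protocol 4.8.2:** give primary-endpoint power separately for Cohort A and Cohort B against combined placebo, with cohort-specific exclusion rates applied to both active and placebo subjects.
- **Synopsis, Protocol 3.1.1 and SAP 2.2 and 2.3:** describe the allocation before and after the switch, and keep the separate rule for a regimen dropped at an interim analysis.

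The cost is wording in the two documents. No added enrolment is needed. The Cohort A power figure may become less favourable.

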4.8.3 Efficacy

4.8.3.1 Primary Efficacy Analysis

The primary objective of this study is to evaluate the effect of MEDI6012 on the reduction of infarct size compared with placebo. The primary efficacy endpoint is infarct size as a percentage of LV mass measured on delayed-enhanced CMR imaging 10-12 weeks post- MI.

The primary efficacy endpoint of infarct size will be analyzed using t-test with log-transformation of the data based on the primary efficacy analysis population.

4.8.3.2 Additional Analyses of the Primary Endpoint

The primary endpoint of infarct size will also be analyzed based on the Efficacy Analysis Population - TIMI 2-3, the Efficacy Analysis Population - TIMI 0-3, and the ITT Population.

4.8.3.3 Secondary Efficacy Analyses

Secondary efficacy endpoints include EF measured by cine MRI at 10-12 weeks post-MI, Change in NCPV in the coronary arteries from index CTA to 10-12 weeks post-MI, and Myocardial mass and left ventricular volumes at end-systole and end-diastole.

EF, myocardial mass, and left ventricular volumes will be analyzed similarly to infarct size without the log-transformation of the data.

Change from index CTA in NCPV will be analyzed using t-test based on CTA analysis population.

4.8.3.4 Exploratory Analyses

The exploratory objectives are to determine whether MEDI6012

█

Incidence of CV death or heart failure and incidence of CV death, MI, unstable angina or urgent coronary revascularization from randomization to final study visit (10-12 weeks post-randomization) will be calculated. Time to first major adverse CV event will be analyzed using log-rank test.

The proportion of TFG at baseline (on initial angiography, pre-PCI) and the proportion of subjects with decline in renal functions at 48 hours will be compared between MEDI6012 and placebo using chi-square test.

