4.6 Treatment Assignment and Blinding

4.6.1 Methods for Assigning Treatment Groups

An IXRS will be used for randomization to a treatment regimen. A subject is considered randomized into the study when the investigator notifies the IXRS that the subject meets eligibility criteria. Subjects will be randomized in a 1:1 ratio to one of 2 cohorts, Cohort A (██████████) and Cohort B (██████████). Within each dose regimen, subjects will be randomized in a 2:1 ratio to receive MEDI6012 or placebo:

Cohort A

- MEDI6012, ████████ (n ~ 180)
- Placebo, ████████ (n ~ 90)

Cohort B

- MEDI6012, ████████ (n ~ 180)
- Placebo, ████████ (n ~ 90)

In the event that a dose regimen is dropped at the interim analysis, subjects will be randomized in a 1:1 ratio to receive MEDI6012 or placebo for the remaining dose regimen.

Infarct location will be controlled during the randomization process, ensuring a similar distribution of anterior vs. non-anterior infarcts between the active and placebo groups. In addition, the distribution of subjects with anterior versus non-anterior MIs will be monitored over the course of the study. The goal is that > 50% of the final randomized population will be anterior MI. Therefore, the number with non-anterior MI will be monitored via the IXRS and capped by the study team.

Investigational product (MEDI6012 or placebo) must be administered as soon as possible before pPCI (preferably > 10 minutes prior) and no later than 4 hours from the time investigational product is reconstituted. If there is a delay in the administration of

investigational product such that it will not be administered within the specified timeframe, the study monitor must be notified immediately.

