2.4 Sample Size

3 STATISTICAL METHODS

3.1 General Considerations

An initial database lock for the purpose of clinical study analysis and reporting will be performed when the last randomized subject completes the Day 70 to 84 visit or is discontinued prior to that visit; if no subjects are ongoing in the Extended Follow-up period, then this database lock will be considered the final database lock for the study.

If subjects are ongoing in the Extended Follow-up period, a second database lock will occur after all subjects who entered the Extended Follow-up period have completed their Week 25,

39, or 52 visits as needed or are discontinued prior to these visits, and this will be considered the final database lock. If the last Extended Follow-up visit occurs before the last Day 70 to 84 visit on the study, the second database lock will not be needed.

The study will be unblinded to the sponsor at the time of initial database lock. The site, subjects, and local CRO personnel will remain blinded to treatment assignment until the final database lock is declared.

Safety data will be generated for the Extended Follow-up period and summarized as an addendum to the clinical study report.

Data will be provided in listings sorted by treatment group and subject number. Tabular summaries will be presented by treatment group with placebo group combined when appropriate. Categorical data will be summarized by the number and percentage of subjects in each category. Continuous variables will be summarized by descriptive statistics. Baseline values will be defined as the last valid assessment prior to the first administration of investigational product on Day 1 unless data are missing, in which case, baseline will be defined as the last value prior to dosing. All statistical tests will be one-sided (based on protocol amendment) at an alpha = 0.05 significance level unless stated otherwise.

Confidence intervals will be one-sided (based on protocol amendment) and nominal p-values will be reported when appropriate.

Data analyses will be conducted using the SAS® System Version 9.3 or higher (SAS Institute Inc., Cary, NC) unless otherwise specified.

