3.4.1.5 Subgroup Analyses

The primary endpoint of infarct size will be analyzed for the following subgroups. The first set of subgroups are based on baseline characteristics and time of treatment administration.

- Sex: male vs female

- Diabetic vs non-diabetic
- Smoker vs non-smoker
- Infarct location: anterior vs non-anterior
- TIMI Flow Grade 0 vs 1 vs 2 vs 3 pre-pPCI
- TIMI Flow Grade 0 or 1 vs 2 or 3 pre-pPCI
- Above vs below the median door-to-device time
- Above vs below the median symptom onset-to-device time
- Above vs below the median symptom onset-to-door time

The second set of subgroups, outlined in Table 3.2, are based on post-randomization outcomes and will not be used to make comparisons between treatment and placebo.

Table 3.2 Post-randomization Analysis Subgroups

Endpoint	Comparison Groups
Infarct size by culprit vessel location determined by baseline invasive coronary angiography	LAD vs Non-LAD LAD vs Left Circumflex Artery vs Right Coronary Artery
Infarct size by timing of drug administration	Investigational product administration before vs after pPCI Above vs below the median time between Dose 1 and pPCI
Infarct size by post-pPCI TIMI Flow Grade	TIMI Flow Grade 0 vs 1 vs 2 vs 3 post-pPCI TIMI Flow Grade 0 or 1 vs 2 or 3 post-pPCI

Infarct size by lipid and apolipoprotein levels	
Above vs. below the median HDL at baseline
 
Above vs. below the median HDL change from baseline
 
Above vs. below the median apoA1 at baseline
 
Above vs. below the median apoA1 change from baseline

Infarct size by cardiovascular event status	
Any CV event vs no CV event
 
HF Hospitalization vs No HF

LAD = left anterior descending artery; pPCI = primary percutaneous coronary intervention; CV = cardiovascular; HF = heart failure

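### A plain chi-square test on pre-PCI TIMI flow, an ordered 0-3 grade, gives up power against an ordered shift; a rank test on the four grades would cost one sentence.

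*Protocol*

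**What the plan says.** Protocol 4.8.3.4 sends two outcomes to one test: "The proportion of TFG at baseline (on initial angiography, pre-PCI) and the proportion of subjects with decline in renal functions at 48 hours". For both outcomes the method named is a chi-square comparison of the arms. The section gives no cut-point, no use of the grade order and no direction for TFG.

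The SAP groups pre-PCI TFG in two ways in its subgroup list (3.4.1.5): "TIMI Flow Grade 0 vs 1 vs 2 vs 3 pre-pPCI" and "TIMI Flow Grade 0 or 1 vs 2 or 3 pre-pPCI". The second grouping also separates two of the analysis populations in SAP 3.2.

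On sidedness, SAP 3.1 sets a default: "All statistical tests will be one-sided (based on protocol amendment) at an alpha = 0.05 significance level unless stated otherwise".

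The text that could define the TFG comparison further (Protocol Table 5, SAP Table 2.3 and SAP 3.4.3) is blacked out or not readable. Its absence is not a fault of the plan.

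**The concern.** A chi-square test on four grades spreads its sensitivity over 3 degrees of freedom. It treats a steady movement from poor to good flow in the same way as an irregular scatter across grades. Collapsing to 0-1 versus 2-3 removes the extra degrees of freedom but discards movement within each half. For a flow grade, an ordered shift is the natural alternative, and neither form is the most sensitive test for it.

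TFG on initial angiography decides who enters the Primary Efficacy Analysis Population (SAP 3.2, TFG 0 or 1). A difference between arms in pre-PCI flow would therefore matter to anyone reading the primary comparison. An insensitive test makes an uninformative result of no difference more likely.

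**Working it through.** **Stated figures.** The plan gives no power, effect size or sample size for TFG, so there is nothing to reproduce for this test. The subject numbers do reconcile: 90 / (1 - 0.5) = 180 per MEDI6012 arm; 2 x 180 + 2 x 90 = 540; 0.6 x 0.5 x 540 = 162, the second interim number.

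**Inputs.**
- Total: "Enrolment of approximately 540 subjects is planned" (Protocol 3.1.2).
- Allocation: "Within each dose regimen, subjects will be randomized in a 2:1 ratio to receive MEDI6012 or placebo" (Protocol 4.6.1), so about 360 versus 180 with regimens pooled. Under Protocol 4.2.1.1 (Amendment 6) the remaining subjects are allocated 1:1, so the final ratio lies between 2:1 and 1:1.
- Share with TFG 0-1: above 60% planned (Protocol 3.2.2). Assumed 60-70% in placebo.
- Effect: assumed common odds ratio (OR) for higher flow of 1.3, 1.5 or 2.0.
- Level: 0.05, two-sided for all three tests, so that the comparison isolates the use of order.

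**Check by formula, one scenario.** Placebo 55/10/15/20% in grades 0/1/2/3. OR 1.5 gives 44.9/10.4/17.4/27.3% on MEDI6012. Pooled 2:1, the proportions are 0.483, 0.103, 0.166 and 0.249.

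1. *3-df chi-square.* Noncentrality = (360 x 180 / 540) x sum of (difference² / pooled proportion) = 120 x (0.0211 + 0.0002 + 0.0035 + 0.0214) = 5.54. Against the 3-df critical value of 7.81, power is 48%.
2. *0-1 versus 2-3.* Placebo 0.35; MEDI6012 0.35 x 1.5 / (0.65 + 0.35 x 1.5) = 0.4468. Difference 0.0968; standard error 0.0450 under the null and 0.0442 under the alternative. Power = Φ((0.0968 - 1.96 x 0.0450) / 0.0442) = Φ(0.20) = 58%.
3. *Rank test on four grades.* Information V = 360 x 180 / (3 x 540) x (1 - sum of cubed pooled proportions) = 40 x (1 - 0.133) = 34.7. Mean z = ln(1.5) x √34.7 = 0.405 x 5.89 = 2.39. Power = Φ(2.39 - 1.96) = Φ(0.43) = 67%.

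The noncentrality in step 1 (5.54) is close to the squared mean z in step 3 (2.39² = 5.7). The signal is nearly the same; the chi-square spends it on 3 degrees of freedom and the rank test on 1.

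**Simulation, 20,000 trials per setting, OR 1.5, 360 versus 180, two-sided power (%).**

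| Placebo TFG 0/1/2/3 (%) | 3-df chi-square | 0-1 vs 2-3 | Rank test |
|---|---|---|---|
| 55/10/15/20 | 48.1 | 58.4 | 65.5 |
| 50/10/17/23 | 49.3 | 59.2 | 67.1 |
| 60/10/13/17 | 45.4 | 55.4 | 63.5 |
| 60/8/12/20 | 45.6 | 54.7-59.4 by formula (this and the next two rows) | 63.8 |
| 50/10/15/25 | 49.2 | | 66.4 |
| 65/5/10/20 | 42.4 | | 60.4 |

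Type I error was close to 0.05 for every test. Repeat runs move the ends by about a point; rounded, the ranges are about 43-50%, 55-59% and 61-67%.

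**Other effects, 360 versus 180.** OR 1.3: about 19-22%, 27-30% and 30-34%. OR 2.0: about 92-95%, 96% and 98%.

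**Other allocations, first distribution, OR 1.5.** 270 versus 270: 54%, 63% and 71%. 180 versus 180 (one regimen against pooled placebo): 38%, 46% and 53%.

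**The case against.** *The four-grade test is not established.* The phrase "The proportion of TFG at baseline (on initial angiography, pre-PCI" gives no categories, it is paired with a binary outcome, and the plan often splits TFG at 0-1 versus 2-3. This stands. On that reading the loss at OR 1.5 falls to roughly 6 to 9 points, but it does not vanish.

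*The advantage depends on an ordered effect.* This also stands. For an assumed non-monotone change (MEDI6012 50/15/20/15% against placebo 55/10/15/20%), the 3-df chi-square has 54% power and the two-sided rank test 7%. That is the reason to keep the four-grade table.

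*As a balance check, a two-sided test is reasonable.* Agreed, but that argues for two-sidedness and not for the chi-square. For a shift towards worse flow (OR 1/1.5), the 3-df chi-square rejects in 47% of trials and the two-sided rank test in 62%; a one-sided test for benefit almost never does.

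*Little depends on it.* The analysis is exploratory, the protocol describes p-values as nominal, and no readable decision rule uses this test. This limits the point to an improvement.

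A reader might infer three stronger things that the documents do not support:
- *That a chi-square cannot follow the one-sided rule.* The rule in SAP 3.1 allows stated exceptions, and the signed root of a 1-df chi-square is a one-sided z-test.
- *That TFG is read after the first dose in nearly all subjects.* Dosing is timed to the first wire crossing the culprit lesion (Protocol 4.5.1.4), not to initial angiography, and Protocol 4.1.7 contemplates angiographic findings before as well as after initial dosing.
- *That this is the only comparison of pre-PCI flow between arms.* SAP 3.4.3 and the details in SAP Table 2.3 cannot be read, so this cannot be known.

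**Conclusion.** The point holds as a low-cost improvement. On either reading of the TFG comparison, a rank test on four grades is more sensitive to an ordered shift. In the 55/10/15/20% scenario at OR 1.5, the gain at equal sidedness is 65.5 - 48.1 = 17 points over the 3-df chi-square and 65.5 - 58.4 = 7 points over the two-group split. The gain is small at OR 2.0, where every test has more than 90% power. Setting a one-sided rank test (76% in the same scenario) against the chi-square would overstate the matter, because about 11 of those points come from direction and not from order.

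These figures rest on assumed TFG distributions, an assumed proportional-odds shift and about 540 subjects with a TFG reading. None includes stratification. The primary analysis is unaffected.

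**What to change.** In Protocol 4.8.3.4 and the matching SAP section:

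1. Compare TFG 0/1/2/3 between arms by a Wilcoxon-type test (Cochran-Mantel-Haenszel row mean scores, van Elteren form), stratified by infarct location, which is the randomization factor (Protocol 4.1.5, SAP 2.3).
2. Report the common odds ratio with its confidence interval.
3. State the sidedness. The row-mean-score statistic for two arms is itself non-directional, so use its signed root if the SAP's one-sided default is to apply; otherwise declare the test two-sided as an exception.
4. Show the four-grade table by arm as description, so that a non-monotone change remains visible.
5. Keep the chi-square for renal decline at 48 hours, with its sidedness stated.

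The cost is a sentence or two of text and one programming option. No new data are needed, and the only statistical price is lower sensitivity to a non-monotone change.
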